6.13.1 Reporting Procedures for Serious Adverse Events

All SAEs related to the PERFORM study or rehabilitation programme (intervention) occurring from the time of written informed consent until the 3 month follow up visit must be reported to the Sponsor immediately and within 24 hours of becoming aware of the event. These related SAEs will be reported using appropriate forms and according to the Sponsor SOP for reporting serious adverse events. Additional information will be provided if requested to the Sponsor and main Research Ethics Committee (REC). The Principal Investigator or another delegated physician (as agreed by the Sponsor) is responsible for

the review and sign off of the SAE and the assessment of causality (i.e. whether an event is related to a study procedure or intervention).

If a delegated clinican from the reporting site is unavailable at the time of identification of a SAE the initial report without assessment of whether the event was related to the study or intervention should be submitted to the Sponsor. This must be completed immediately and within 24 hours of the study team becoming aware of the SAE, and must be followed-up by medical assessment as soon as possible thereafter.

The Sponsor will perform an initial check of the information and ensure that the SAE line listing is reviewed by the Director of Research & Innovation. All SAE information must be recorded on an SAE form and sent to the Sponsor. Additional information received for a case (follow-up or corrections to the original case) needs to be detailed on a new SAE form and sent to the Sponsor.

Copies of all documentation and correspondence relating to SAEs will be stored in the TMF and / or ISF

For each SAE the following information will be collected:

- a) full details in medical terms and case description
- b) event duration (start and end dates, if applicable)
- c) action taken
- d) outcome
- e) seriousness criteria
- f) relationship to the study procedure or intervention

Any change of condition or other follow-up information should be emailed to the Sponsor as soon as it is available or at least within 24 hours of the information becoming available. Events will be followed up until the event has resolved or a final outcome has been reached."

The Sponsor will report all SUSARs to the Research Ethics Committee concerned. Fatal or life-threatening SUSARs must be reported within 7 days and all other SUSARs within 15 days. The CI will inform all investigators concerned of relevant information about SUSARs that could adversely affect the safety of participants.

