5.2 Exclusion Criteria

Individuals will be excluded for the following:

- Unable to give consent for the study
- Unable to communicate in English (carer or support worker may be available)
- Known contraindications to exercise (as defined by the American College of Sports Medicine) ("ACSM's guidelines for exercise testing and prescription 11th Ed. 2021.") to include
 - Unstable cardiac disease
 - Current fever
 - Significant aortic aneurysm (more than 5.5 cm)
- Unable to attend in-person training sessions
- Participation in a exercised rehabilitation programme in the last 6 months.
- Unstable psychiatric disorder that limits or disrupts group based interventions.
- On an End of Life pathway with a prognosis of less than 12 months survival.
- Active malignancy (on chemotherapy/radiotherapy/planned urgent surgery)
- For people on a surgical waiting list a pragmatic decision will be made on a case by case basis of the type of surgery, urgency and likely wait times.
- Pregnant women
- Under 18's
- Living in a Nursing Home.
- Unsafe to exercise in a group without 1:1 supervision (e.g. significant risk of falls)

6. STUDY PROCEDURES 6.1 Schedule of Procedures

| | Feasibility Study Visits | | | | | | | |
|--|--------------------------|------------------------------|--|---|--|---|--|--|
| Procedures | Pre Screening | Screening and Baseline | Intervention Phase (within 4 weeks of randomisation) | Discharge appointment (1 -2 weeks after completion of Intervention) | 3-Month Follow-Up (3 months post- randomisation ± 4 weeks) | Optional Interviews (after completion of Intervention Phase for participants) | 4 month group maintenance Session (Intervention patients only 4 month post randomisation) | 6 month group maintenance Session (Intervention patients only 6 month post randomisation) |
| Invitation | Х | | | | | | | |
| Eligibility assessment | | Х | | | | | | |
| Informed consent | | Х | | | | | | |
| Randomisation | | Х | | | | | | |
| Baseline assessments | | Х | | | | | | |
| Intervention or control | | | Х | | | | | |
| Intervention discharge assessment | | | | X | | | | |
| Outcome questionnaires | | Х | | | Х | | | |
| Follow-up assessments | | | | | Х | | | |
| Resource use data collection questionnaire | | | | | Х | | | |
| Patient & provider interviews | | | | | | Х | | |
| Maintenance session | | | | | | | Х | Х |

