6.8.3 Follow-up assessments

Follow up will be undertaken at 3-month follow up (3 months post randomisation).

 All measures identified above will be repeated. All outcome measures will be conducted by a blinded assessor who will have no knowledge of previous test results or treatment allocation.

6.8.4 4 and 6 month group maintenance sessions

Patients randomised to the PERFORM intervention exercise programme will be invited to attend 2 group maintenance sessions at 4 months post randomisation and 6 month post randomisation. These sessions will provide an opportunity provide additional support to participants, review long-term progress and address any further questions they may have.

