6.11 End of trial

This study will end when the specified number of participants have been recruited, all participants have completed their last follow up visit, data validation has taken place and the database is locked and statistical analysis complete.

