7. INTERVENTION & CONTROL

7.1 Intervention group

The PERFORM rehabilitation programme will comprise an 8 week supervised rehabilitation programme, 6 weeks, twice weekly then 2 weeks, once a week that will be offered in either a primary or secondary care setting. Each session will last for 2 hours (1hr of 'move and improve

exercise sessions, and 1hr patient 'Health and Wellbeing' self care support session and Q&A/opportunity to interact with the group). The intervention will be offered within 4 weeks of randomisation.

The rehabilitation programme will comprise an exercise component with an accompanying education programme. The 'Health and Wellbeing' self care support sessions / educational package will offer advice and support for behaviour change to support positive lifestyle changes and symptom management. Much of the advice will be appropriate to all participants for example health eating, the benefits of exercise, stress management and relaxation techniques, medicines adherence, and exacerbation of symptoms. The aim of the education 'health and wellbeing' package is to support symptom management, risk factor management and enhance self-management skills. The education programme will be delivered by healthcare professionals delivered as informal and interactive sessions. The information will be supplemented by written leaflets and material to support the individual to share with their family and carers. After the 8 week programme the participant will have a discharge appointment in most cases this will take place 1-2 weeks following the last rehabilitation session.

Each 'move and improve' exercise session will offer an individually prescribed and progressed aerobic walking programme (a combination of walking (treadmill where available). In addition resistance training will be delivered that will be individually prescribed and progressed.

Participants will also be encouraged to complete a home exercise programme that will be closely monitored. A home exercise booklet will be provided as well as a progress tracker standardised exercise diary that will ask participants to record exercise frequency, duration and symptom scores post bout of exercise. This will be recorded for the aerobic and resistance programme.

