Participants are then invited to take part in 2 further group maintenance sessions, one 4 months after randomisation and one 6 months after randomisation, this will give participants the opportunity to review their long-term progress and address any further questions. After these visits the participant will return to their usual care.

There is no national benchmarking for staff to participant ratio, but we will take guidance from the pulmonary and cardiac rehabilitation standards recommending a minimum of 1:8 ratio, with a minimum of two healthcare professionals in any session.

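### Mandatory sponsor reporting of related SAEs stops at the 3-month visit, before the 4- and 6-month maintenance sessions and possibly before the supervised programme ends

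*Protocol*

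**What the plan says.** **Reporting window.** Protocol section 6.13.1 states that SAEs related to the study or the programme, "occurring from the time of written informed consent until the 3 month follow up visit must be reported to the Sponsor". The deadline is 24 hours after the site learns of the event.

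**Date of the closing visit.** The schedule of procedures (section 6.1) allows a tolerance: "3-Month Follow-Up (3 months post- randomisation ± 4 weeks".

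**Sessions after that visit.** Section 7.1 (Intervention group) provides for "2 further group maintenance sessions, one 4 months after randomisation and one 6 months after randomisation". Section 6.8.4 limits them to one arm: "Patients randomised to the PERFORM intervention exercise programme will be invited to attend 2 group maintenance sessions". Section 7.1 adds: "After these visits the participant will return to their usual care". Section 3 and the schedule carry the same two sessions.

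**Main programme.** Section 7.1 describes 8 weeks of supervised rehabilitation and says: "The intervention will be offered within 4 weeks of randomisation". A discharge appointment follows, usually 1 to 2 weeks after the last session.

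**Other safety provisions.** The definitions in section 6.13 provide for logging of related AEs and for PSC and Sponsor review of related SAEs. Section 10.5 has SAEs monitored for the whole study. Section 11.2 has related events entered in the hospital notes. None of these gives an end date.

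**The concern.** The protocol already restricts reporting to events judged related to the programme or to study assessments. Section 6.13.1 then lifts the duty to report even those events at a visit that comes before the study has finished delivering sessions to the intervention arm. A site following 6.13.1 literally would not send the Sponsor a related SAE arising from a maintenance session. A site following section 10.5 might.

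Two things are at stake. One is prompt notice to the Sponsor, which is where the SAE form and line listing begin. The other is consistent ascertainment across sites of the harms that will inform the main trial. The co-primary progression criteria (recruitment, retention, attendance) do not use SAE data, so no feasibility conclusion changes.

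The tolerance on the 3-month visit adds a second problem. The cut-off is tied to a visit that may be held early, while the start of the programme may be late. The window can then close during supervised exercise.

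**Working it through.** The plan gives no figure to reproduce, so the check is a timeline counted from randomisation.

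**Inputs**
- 3-month visit: 3 months ± 4 weeks (section 6.1).
- Maintenance sessions: 4 and 6 months (sections 6.8.4 and 7.1).
- Main programme: offered within 4 weeks, lasting 8 weeks (section 7.1).
- Intervention arm: 40 participants (sections 3 and 10.1).
- Convention: 1 month = 365.25 / 12 = 30.44 days.

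**When the window closes**
- Nominal: 3 × 30.44 = day 91.3.
- Earliest: 91.3 − 28 = day 63.3.
- Latest: 91.3 + 28 = day 119.3.

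**When the maintenance sessions fall**
- 4 months: 4 × 30.44 = day 121.8.
- 6 months: 6 × 30.44 = day 182.6.

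**Days from closure of the window to each session**

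| 3-month visit held | to 4-month session | to 6-month session |
|---|---|---|
| Earliest (day 63.3) | 58.4 | 119.3 |
| Nominal (day 91.3) | 30.4 | 91.3 |
| Latest (day 119.3) | 2.4 | 63.3 |

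Every gap is positive. The tightest one, 2.4 days on average months, was repeated on calendar dates for every randomisation day from June 2023 to June 2024. It then ranges from 1 to 3 days and never reaches zero. At their stated times, both sessions always fall after the cut-off.

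**Upper bound on sessions affected:** 40 participants × 2 sessions = 80 participant-sessions. This counts invitations, so attendance can only lower it.

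**Main programme against an early 3-month visit**
- Latest end of supervised sessions: 28 + 56 = day 84.
- Shortfall if the visit is at its early limit: 84 − 63.3 = 20.7 days, or 20.7 / 7 = about 3 weeks.
- Discharge appointment in that case: 84 + 7 to 84 + 14 = day 91 to 98, also after closure.

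This second gap is a worst case that combines a late start with an early visit. It is permitted by the stated windows and it concerns prescribed aerobic and resistance training.

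**Passages side by side.** Section 6.13.1 has an end date. Sections 6.13 (definitions), 10.5 and 11.2 cover related events with none. Both rules cannot govern a related SAE at month 5.

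**The case against.** The strongest reply is that this is an inconsistency within the protocol and not a hole in safety oversight. Logging of related AEs, PSC and Sponsor review of related SAEs, SUSAR reporting to the ethics committee, monitoring throughout the study and entry in the notes all lack a cut-off. That stands. A reader might infer that related events after 3 months need not reach the ethics or steering committee, but the documents do not support this. The clause with a cut-off is the one on sponsor reporting. The open-ended provisions still do not settle the matter, because they conflict with the one clause that tells sites when to report.

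The second reply concerns exposure. Sections 6.8.4 and 7.1 describe the maintenance sessions as support, progress review and questions, and state no exercise. This also stands, and the added risk may be small. To describe the uncovered time as half of the six months of intervention contact would mislead, since it contains two group sessions. The reply does not reach the early-visit gap, which involves supervised exercise.

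A reader might also infer that the trial could be declared over before the last session, because section 6.11 requires that "all participants have completed their last follow up visit, data validation has taken place". That section names no time point, and the Trial Summary lists the 4- and 6-month sessions in its row on follow-up duration. Section 6.11 further requires database lock and completed analysis. The term is at most ambiguous.

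Finally, the amendment history shows that the maintenance visits came in with version 2.0. An overlooked SAE clause would explain the mismatch, but the documents do not say that this happened.

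**Conclusion.** The point holds as a contradiction in the reporting rule that should be fixed. Mandatory 24-hour sponsor reporting of related SAEs ends between about day 63 and day 119, while study-delivered sessions are scheduled at about days 122 and 183. In the worst permitted case the rule also ends about 3 weeks before supervised exercise does. The loss is confined to expedited sponsor reporting.

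The conclusion assumes that the maintenance sessions are held at their stated times. They have no visit window of their own, so one held early could precede a late 3-month visit. It also assumes that the programme starts no later than 4 weeks after randomisation; a later start would widen the early-visit gap.

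**What to change.** Reconcile section 6.13.1 with sections 6.8.4, 7.1, 6.13 (definitions), 10.5 and 11.2. Run the related-SAE reporting window to the later of the 3-month visit and the participant's last study-delivered session. For PERFORM participants who attend it, that is the 6-month maintenance session. The wording should make clear that an event attributed to that last session is included. This rule also closes the early-visit gap.

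In the analysis, keep the between-arm SAE table on the common period from consent to the 3-month visit, and list later intervention-arm events separately. Only one arm attends the later sessions, so a pooled count over the longer window would compare unequal ascertainment.

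The cost is a wording amendment and slightly longer reporting in one arm. No visit is added, because the sessions are already scheduled.

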6.14 Reporting urgent safety measures

If any urgent safety measures are taken the CI/Sponsor shall immediately and in any event no later than 3 days from the date the measures are taken, give written notice to the Sponsor and the relevant REC of the measures taken and the circumstances giving rise to those measures

7. INTERVENTION & CONTROL

7.1 Intervention group

The PERFORM rehabilitation programme will comprise an 8 week supervised rehabilitation programme, 6 weeks, twice weekly then 2 weeks, once a week that will be offered in either a primary or secondary care setting. Each session will last for 2 hours (1hr of 'move and improve

exercise sessions, and 1hr patient 'Health and Wellbeing' self care support session and Q&A/opportunity to interact with the group). The intervention will be offered within 4 weeks of randomisation.

The rehabilitation programme will comprise an exercise component with an accompanying education programme. The 'Health and Wellbeing' self care support sessions / educational package will offer advice and support for behaviour change to support positive lifestyle changes and symptom management. Much of the advice will be appropriate to all participants for example health eating, the benefits of exercise, stress management and relaxation techniques, medicines adherence, and exacerbation of symptoms. The aim of the education 'health and wellbeing' package is to support symptom management, risk factor management and enhance self-management skills. The education programme will be delivered by healthcare professionals delivered as informal and interactive sessions. The information will be supplemented by written leaflets and material to support the individual to share with their family and carers. After the 8 week programme the participant will have a discharge appointment in most cases this will take place 1-2 weeks following the last rehabilitation session.

Each 'move and improve' exercise session will offer an individually prescribed and progressed aerobic walking programme (a combination of walking (treadmill where available). In addition resistance training will be delivered that will be individually prescribed and progressed.

Participants will also be encouraged to complete a home exercise programme that will be closely monitored. A home exercise booklet will be provided as well as a progress tracker standardised exercise diary that will ask participants to record exercise frequency, duration and symptom scores post bout of exercise. This will be recorded for the aerobic and resistance programme.

Participants are then invited to take part in 2 further group maintenance sessions, one 4 months after randomisation and one 6 months after randomisation, this will give participants the opportunity to review their long-term progress and address any further questions. After these visits the participant will return to their usual care.

There is no national benchmarking for staff to participant ratio, but we will take guidance from the pulmonary and cardiac rehabilitation standards recommending a minimum of 1:8 ratio, with a minimum of two healthcare professionals in any session.

7.2 Control group

Both intervention and control groups will receive usual care, i.e. continue to manage their disease as advised by their primary/secondary care team. This will be continuation with usual medication and follow up visits at either primary or secondary care as scheduled. After the initial assessment, patients allocated to control will continue with their usual care alone.

8. PROCESS EVALUATION

The process evaluation will explore in detail, the feasibility and acceptability of both the intervention, and the study design and it will be conducted following the Medical Research Council guidelines for process evaluation of complex interventions. (64) We will develop a Process Evaluation Framework and Qualitative Analysis Plan to guide data collection and

analyses. A key aim of the process evaluation will be to assess and refine the programme theory in preparation for a full trial. In addition, it will assess: (i) intervention elements, i.e. acceptability, context, fidelity, exposure, reach and (ii) study related elements i.e. acceptability of study methods including recruitment, outcome measures and contamination.

Quantitative process data will include attendance at sessions and fidelity assessments. The fidelity assessment will be completed using randomly selected audio and video recorded sessions and a fidelity checklist developed by the study team, building on methods used in our prior intervention studies.(65) We will assess 24 individual initial assessments and 24 followup/discharge visits (n=8 per site). We will assess (by direct observation/researcher site visit) 6-9 of the group exercise sessions (2-3 visits per site), these will include a mixture of early, mid and late sessions per group. Finally, we will audio record all (where possible and where all participants of the group have consented) of the 'Health and Wellbeing' self care support sessions and assess a sample of 24-30 of these (8-10 per site), reflecting the full range of session-topics. Two team members will rate these sessions and inter-rater reliability will be assessed using Gwet's AC1. (66) We will also: (i) ask therapists to report confirmation that intended content (exercises, self-care topics, facilitation techniques) were taught, (ii) ask therapists to report both clinic observations of adherence to exercise and their assessment of home exercises performed by patients unsupervised, and (iii) patient reports of exercise adherence (based on completion of a weekly Progress Tracker diary during the first 12 weeks of the intervention). (67) Quantitative process evaluation data will be presented descriptively using mean (standard deviation) and median (interguartile range) for continuous variables and count (percentage) for categorical variables.

Qualitative process data will include semi-structured telephone interviews with patients ($n\sim30$) and staff ($n\sim12$). Patients will be purposively sampled to include a range of conditions, gender, age, socioeconomic status and engagement with the intervention. We will also aim to interview those who did not attend the intervention or those who were low attenders to inform improvements to the intervention. We will recruit from study participants who will be asked to consent to being contacted about the interviews as part of the baseline assessment. They will then be contacted to see if they are willing to take part in the interviews. Two intervention staff and two referrers per site (n=6) will be interviewed to inform recruitment for the main study and identify any implementation issues.

Interviews will take place after the intervention is completed and will explore the acceptability of the recruitment process and outcome measures; acceptability of the intervention; impact of the intervention on behaviour; barriers and facilitators to engagement, staff training, suggestions for improvements as well as contextual factors influencing intervention impact. Interview schedules will be guided by the programme theory and Normalization Process Theory (NPT), an implementation theory that has been used extensively to explore the processes underpinning implementation, embedding and integration of service innovations. We will explore potential mechanisms of intervention effectiveness and of engagement with the intervention. Interviews will be audio recorded and transcribed verbatim.

Qualitative data will be analysed using thematic analysis (68). Themes identified from intervention staff data regarding intervention delivery will be conceptualised through a NPT lens (69) and the patient data through a theoretical lens based on NPT and the programme theory/logic model. Recommendations for refining/improving the intervention will be summarised and used to refine the intervention materials and the facilitator-training course as well as updating the programme theory. Participant quantitative outcomes will be summarised descriptively (e.g. means & standard deviations) by intervention and control group at baseline and follow up.

